## 2) Superiority test of DOAC

If noninferiority of DOAC is demonstrated, a superiority test of DOAC will be performed using a one-sided 0.05 significance level and the same two-sided 90% CI for the difference in the event rate of the primary endpoint at 6 months as used for the noninferiority test. When the upper bound of the CI is less than 0, we will conclude that DOAC therapy is superior to LMWH/warfarin in terms of VTE prevention. Because we will perform the superiority test only after the noninferiority of DOAC is demonstrated, the overall type I error rate is maintained at the 0.05 level (one-sided) without splitting alpha.

### 3.5.2.2. *Planned Interim Analyses*

This study design incorporates several interim analyses and one final analysis for the comparison of the primary endpoint. A 90% two-sided repeated confidence interval (RCI) for the difference in the cumulative incidence rate of VTE at 6 months (DOAC minus Usual Care) between two arms was estimated. We use the critical values based on the Lan-DeMets error spending function corresponding to the truncated version of O'Brien-Fleming boundaries.

Prior to the final analysis, four interim analyses were conducted on September 7, 2018, March 22, 2019, September 9, 2019, and March 25, 2020. Given these interim analyses, the critical value for the final analysis will be 1.710, which corresponds to a one-sided 0.0436 alpha. The confidence coefficient of the 90% two-sided RCI will be 91.28% for the final analysis.

### 3.5.2.3. *Secondary analyses of the primary endpoint*

#### 1) Analysis with other summary measures

The absolute difference in 6-month event rate based on the cumulative incidence function (CIF) is the primary summary measure of the between-group difference. As a secondary analysis, we will calculate a subhazard ratio using the Fine and Gray model. We will construct 0.90 CIs for these measures.

#### 2) Alternative way to handle deaths

In the primary analysis, we handle deaths as competing risks and estimate the recurrent VTE rates by the CIF approach. As a secondary analysis, we will handle deaths as censored observations and estimate the recurrent VTE event rates by the Kaplan-Meier method. We will calculate the hazard ratio and difference in the event rate at 6 months and corresponding 0.90 CIs.

### 3) Sensitivity Analyses including data from the preference cohort

This study allowed a limited number of participants to enroll in the preference cohort if an eligible participant declines randomization. The Preference Cohort Closing Rules were pre-specified in Section 13.2.2 in the study protocol to specify the maximum number of participants enrolled in the preference cohort and to avoid an extreme imbalance of the number of participants between two groups. The results of monthly data monitoring in June 2017 observed the pre-set imbalance criteria in between arm selection. The enrollment to the preference cohort was therefore closed in December 2017, after 140 patients had enrolled in it.

First, we will compare characteristics between the preference and randomized cohorts to assess potential heterogeneity between the two cohorts. Fisher's exact test will be used for nominal categorical variables, and two-sample Wilcoxon tests will be used for ordered categorical or continuous variables.

We will estimate the difference in VTE event rate at 6 months and its standard error from the preference cohort, using a propensity score approach to adjust for potential treatment selection. We will then combine the result with that from the randomized cohort, using a weighted average. An optimal weight (i.e., the reciprocals of the variance) will be used. The resulting estimate for the difference in VTE event rate and 90% CI can be considered an overall average treatment effect of DOAC across the full cohort. In no circumstance will analyses of the full cohort be presented as primary.

### 4) Analysis by type of VTE recurrence

We will also conduct the same analyses for each of the following subtypes of VTE recurrence.

- 1) Pulmonary embolism (PE) with or without deep vein thrombosis (DVT)
- 2) DVT without PE

### 5) Adjusted analyses

We will perform adjusted analysis to estimate the adjusted treatment effect, using generalized linear mixed-effects models with the logit link. Censored observations will be handled by the inverse probability censoring weight technique. The participating sites will be included as random-effects. Those baseline characteristics variables (see 3.4) whose distributions are not balanced between two groups ( $p<0.05$ ) in the randomization cohort will be included as fixed-effects in the models for adjustment.

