## 6.1 Stratification Factors and Treatment Assignments

### 6.1.1 Stratification Factors – None

### 6.1.2 Treatment Assignments

Participants will be randomized 1:1 to either

- **ARM 1 – Intervention Arm, DOAC** (choice of rivaroxaban, apixaban, edoxaban, or dabigatran)
- **ARM 2 – Usual Care Arm, LMWH/warfarin** (choice of LMWH with or without a transition to warfarin)

*If an eligible participant is offered randomization and **declines** randomization\*\*, then a limited number of participants (up to N=190) will be allowed to enroll in the Preference Cohort. In this case, the treating physician and patient will choose protocol treatment on Arm 1 or Arm 2 (non-randomized).\*\**

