## 2.4. Randomization and stratification criteria

If an eligible participant was offered randomization and declined to be randomized, then a limited number of participants were allowed to enroll in the Preference Cohort, where the treating physician and patient chose protocol treatment on Arm 1 or Arm 2.

Participants who agreed to be randomized or participants who entered after the closure of the preference cohort were randomized 1:1 to either:

**Arm 1 – Intervention Arm, DOAC** (choice of rivaroxaban, apixaban, edoxaban, or dabigatran)

**Arm 2 – Usual Care Arm, LMWH/warfarin** (choice of LMWH with or without a transition to warfarin)

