### 3.4. Baseline demographic and disease characteristics

Baseline patient characteristics and disease characteristics listed below will be summarized using descriptive statistics by group. The two-sample Wilcoxon test will be used for between-group comparisons of continuous variables and ordered categorical variables, and Fisher's exact test will be used for nominal categorical variables.

List of the variables:

- Age at enrollment [year]
- Age category (<65, >=65 year old)
- Sex (Male/Female)
- Race (Native American or Alaska Native/Asian/Black or African American/Native Hawaiian or other Pacific Islander/White/Unknown)
- Ethnicity (Hispanic or Latino/Not Hispanic/Unknown)
- Height [cm]
- Weight [kg]
- BMI
- Education level (Grade school or less/high school or GED/Some vocational, business or trade school/some college/college/some graduate school/graduate or professional degree)
- Whether out-of-pocket costs of anti-clotting drugs affect decision to participate in the study (not at all/a little/moderate/quite a bit/extremely)
- Payment (Private insurance/Medicare/Medicaid/Military or Veterans Sponsored/Self Pay/Other/Unknown)
- ECOG performance status (0/1/2/3/4)
- Smoking status (current/former/never)
- Cancer ever metastasized (Yes/No)
- HighlyThrombogenetic Tumors (Yes/No)
- Indwelling Central Venous Catheters (Yes/No)
- Thrombocytopenia (Yes/No) (<150,000/mm^3)
- Creatinine Clearance [ml/min] (Gender-specific Normal/abnormal)
- Albumin [g/dL] (<3.5mg/dL vs. >=3.5mg/dL)
- Self described global health status at baseline (excellent/very good/good/fair/poor)
- Current cancer Type (solid cancer vs hematologic cancer)
- Current cancer Subtype (Leukemia/Lymphomas/Blood Disorders, Breast, Gastrointestinal and Digestive, Gynecologic, Head and Neck, Neurological (Brain), Sarcoma, Skin/Melanoma, Thoracic (Chest/Lung), Genitourinary, Other)
- AJCC cancer stage at diagnosis (0, I, II, III, IV, Not applicable)
- Blood clot type (PE, DVT, Both, Unknown)
- The part(s) of the body where the blood clot found
  - Lung (Yes/No)
  - Leg (Yes/No)
  - Arm (Yes/No)

- Other (Yes/No)
- Site of index VTE diagnosis (inpatient hospital stay/outpatient appointment/emergency department/home/other)
- Site of index VTE first treatment (inpatient hospital stay/outpatient appointment/emergency department/home/other)
- First index VTE treatment prescribed (Warfarin/Dalteparin/Enoxaparin/Fondaparinux/Heparin/Other oral medication/Other injectable medication/Unknown)

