#### 1) Noninferiority test of DOAC

The hypothesis for testing the noninferiority of the DOAC strategy is that the difference in the primary endpoint at 6 months is no greater than a noninferiority margin of 3% for the intervention-comparator. This noninferiority margin was selected based on what is acceptable to patients based on patient-stakeholder input as well as on input provided by clinicians

To confirm the noninferiority hypothesis, we will construct a two-sided 90% confidence interval (CI) for the difference in the cumulative incidence of the primary endpoint at 6 months (180 days). If the upper bound of the CI is less than 3%, we will conclude that the DOAC management strategy is non-inferior to the LMWH/warfarin strategy for management of VTE in patients with cancer.

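### The secondary adjusted analysis picks covariates by baseline p<0.05 instead of prognosis, and its logit output is given no route back to the 3-point risk-difference scale

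*Combined protocol and SAP*

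**What the plan says.** SAP 3.5.2.3 item 5, repeated in protocol 13.3.3 item 5, estimates an adjusted treatment effect "using generalized linear mixed-effects models with the logit link", with inverse probability of censoring weights. On site it states: "The participating sites will be included as random-effects". The fixed effects are the SAP 3.4 baseline variables "whose distributions are not balanced between two groups", judged at p<0.05 in the randomized cohort.

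The p-values come from SAP 3.4, which uses the two-sample Wilcoxon test for continuous and ordered variables; for the rest, "Fisher's exact test will be used for nominal categorical variables". No covariate is named in advance. The design supplies none either, since protocol 6.1 reads "Stratification Factors – None" and patients "were randomized 1:1 to either" arm.

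The noninferiority test (SAP 3.5.2.1) uses "a noninferiority margin of 3% for the intervention-comparator", applied to the difference in 6-month cumulative incidence. SAP 3.5.2.3 item 1 confirms that this absolute difference is the primary summary measure. Neither document gives an odds-ratio margin or a step from the logit model to a risk difference.

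**The concern.** Two features weaken the analysis.

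**Selection.** A baseline p-value measures how far the arms differ, not whether the variable predicts recurrence. Bias or gain from adjustment depends on both. Payment type, education or height can enter by chance, while variables the SAP itself links to VTE risk stay out: highly thrombogenic tumors (3.9.1), central venous catheters (3.9.2, where only a slight increase is expected) and low platelets (3.9.3). Overlapping entries, such as age with age category, or height and weight with BMI, can enter together.

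**Scale.** The treatment coefficient of a logit mixed model is a log odds ratio, conditional on site and covariates. The margin is an absolute difference. A reader who wants to know whether adjustment changes the noninferiority picture gets a number on another scale.

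The choice carries further, because the same analyses are repeated by VTE type, in the ITT and per-protocol sets, for major bleeding (which has its own absolute 2.5% margin) and in subgroups. If screening is redone each time, the covariates can change from one set to the next, and a change of population is mixed with a change of model.

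**Working it through.** **The plan's own figures.** None is given for the adjusted analysis. The nearest checkable one is the final critical value of 1.710 (SAP 3.5.2.2): 1 − Φ(1.710) = 0.0436, and 1 − 2 × 0.0436 = 0.9128, both as stated. The power table (SAP 2.5) cannot be recomputed from stated inputs because it gives no event rates. The point does not depend on it.

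**Chance flags.** SAP 3.4 lists 33 variables, counting the four clot-location items separately (30 if counted as one).
- Expected flags: 33 × 0.05 = 1.65 (30 × 0.05 = 1.5). Correlation between variables does not change this mean. Fisher's test is conservative and lowers it somewhat.
- At least one flag, if independent: 1 − 0.95^33 = 0.82 (1 − 0.95^30 = 0.79).
- At least two, if independent: 0.50 (0.45 with 30).

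**Prognostic variables missed.** Under randomization a given variable is flagged about 5% of the time, however strongly it predicts recurrence. For three independent predictors, the chance that none is flagged is 0.95^3 = 0.857. A simulation of 3,000 null trials (671 patients, 33 independent covariates, three prognostic, no site effect or censoring) gave 0.85.

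**Type I error.** In the same simulation, rejection at a nominal two-sided 10% was 9.5% unadjusted, 9.2% under the p<0.05 rule and 9.4% with the three predictors prespecified. The simulation error is about √(0.1 × 0.9 / 3000) = 0.5 points, so these do not differ.

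**Precision.** A second simulation (1,500 trials, 671 patients) assumed a 4.8% event rate, three predictors with odds ratio 2.5 and 30 noise variables. None of these inputs is in the documents. Relative to no adjustment, the variance of the risk difference was 1.006 under the rule and 0.975 with the predictors prespecified. Applied to the stated 6.1% CI length, 6.1 × √0.975 = 6.02. Noninferiority power of 0.900 becomes Φ[(1.645 + 1.282)/√0.975 − 1.645] ≈ 0.906.

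**Scale.** At control risk p, the 3-point margin as an odds ratio is [(p + 0.03)/(1 − p − 0.03)] / [p/(1 − p)]. The documents state no control rate for this trial, so p is an assumed range:

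| Assumed control risk | Margin as odds ratio | Risk change at odds ratio 1.50 |
|---|---|---|
| 3% | 2.06 | +1.4 points |
| 6% | 1.55 | +2.7 points |
| 9% | 1.38 | +3.9 points |
| 17% | 1.22 | +6.5 points |

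An odds ratio of 1.50 is inside the margin at 6% and outside it at 9%. This is the marginal conversion; a site- and covariate-conditional odds ratio must also be averaged over patients.

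**Room for covariates.** At assumed event rates of 5% to 7%, 671 patients give 671 × 0.05 = 34 to 671 × 0.07 = 47 events, and fewer in the modified ITT set. That supports four or five covariates, not a long list.

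**The case against.** The strongest reply is that nothing decisive rests here. Noninferiority is decided by the cumulative incidence difference, and this is item 5 of six secondary analyses. Error is not inflated, and prespecified covariates would shorten the CI only from 6.1 to about 6.0 points. All of that stands and limits the weight of the point.

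Four stronger readings are tempting, and the documents do not support them.
- *The flags are pure chance.* That holds for all randomized patients. The primary population is the modified ITT set, which drops patients who did not receive the assigned strategy, so an imbalance there can reflect selection and the rule might catch it. The text refers only to the randomized cohort, which leaves the screened population open. The simulations included no such exclusions.
- *The model adjusts only for noise.* Site is always included.
- *The adjusted result can never be set against the margin.* A logit model can yield a risk difference by averaging predicted risks. The plan does not say this will be done; the gap is in the specification. Other supportive analyses also use relative measures (a subhazard ratio and a hazard ratio), so not every secondary result is meant as a margin test.
- *This is the plan's safeguard against baseline imbalance.* The text states no such purpose.

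It can also be said that the plan does not ignore the prognostic variables, since several define planned subgroups. That is true, but subgroup estimates are not adjustment.

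**Conclusion.** The point holds as one about a supportive analysis that should be improved. The selection rule is stated, not merely left open, and it selects on the wrong property: about 1.65 chance flags among 33 variables, an 82% chance of at least one under independence, and roughly an 85% chance that none of three true predictors enters. As specified, the output is not on the scale of the margin, which corresponds to odds ratios from 2.06 to 1.22 over assumed control risks of 3% to 17%.

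The cost lies in interpretation and in adjusting for the wrong variables. It does not reach the primary conclusion or the error rate, and the precision forgone is about 2.5% of variance under assumed inputs. The counts rest on randomization holding in the screened set; in the modified ITT set they are a guide only.

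**What to change.** In SAP 3.5.2.3 item 5 and protocol 13.3.3 item 5, replace the p<0.05 sentence with a fixed list of about four or five prognostic covariates from SAP 3.4, for example highly thrombogenic tumor, central venous catheter, platelets below 150,000, cancer ever metastasized and previous VTE. Keep the random site effect. Set the list before outcomes are compared by arm in the final analysis. Four interim comparisons have already been run, so the choice should rest on clinical prognosis alone. Use the same list in every analysis population, which also removes the question of which set is screened.

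From the fitted model, report the standardized 6-month risk difference (predicted risk averaged over all patients under each arm) next to the odds ratio. Give its CI at the final-analysis level of 91.28% (SAP 3.5.2.2), and name that level explicitly because SAP 3.5.2.1 speaks of 90%.

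The cost is a change of wording and a few lines of code. The covariates are already collected. The small downside is being committed to the list in advance.

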### 6) Sensitivity Analyses using the ITT and the per protocol populations.

Sensitivity analyses will be performed with alternative cohort specification.

We will repeat all the analyses using the ITT population and then using the per-protocol population.

## 3.6. Secondary endpoint evaluation

### 3.6.1. Secondary endpoints

- Cumulative incidence of major bleeding reported by either patients or clinicians at 6 months
- Cumulative incidence of all bleeding events and bleeding according to its severity in the following categories: 1) major bleeding, 2) clinically significant non-major and 3) nuisance
- Cumulative incidence of death at 6 months
- Overall HRQOL at 3 and 6 months
- Overall score on the Anti-Clot Therapy Scale at 3 and 6 months

### 3.6.2. Analyses for secondary endpoints

- 1) *Cumulative rates of major bleeding reported by patients or clinicians at 6 months (grade 3, 4, or 5)*

We will repeat the analogous analyses as performed for the primary endpoint (see 3.5.2). The primary analysis plan for major bleeding, fatal or non-fatal, is also based on the sequential evaluation of noninferiority and superiority. We will construct a two-sided 90% CI for the difference in the cumulative incidence rate for the composite outcomes of major bleeding and death. If the upper bound of the CI is less than 2.5%, we will conclude that DOAC is noninferior to LMWH/warfarin in terms of major bleeding. The same secondary analyses as planned for the primary endpoint will be performed. In contrast to clotting, fatal bleeding events are usually clinically manifest and recorded and therefore can be distinguished.

- 2) *Cumulative incidence of all bleeding events reported by patients or clinicians at 6 months in the following categories: 1) major bleeding (Grade >=3), 2) clinically significant non-major (Grade 2); and, 3) nuisance bleeding (Grade 1)*

Clinically significant non-major bleeding is defined as Grade 2 Nuisance bleeding is defined as Grade 1 according to the NCI CTCAE criteria. We will perform the same analyses as described for major bleeding.

- 3) *Mortality*

Time from randomization to death from any cause is a secondary endpoint. The study is powered to confirm the primary hypothesis for recurrent VTE; we do not anticipate enough power to perform a confirmatory analysis for all-cause mortality. We will instead focus on providing quantitative information for the between-group difference for this endpoint. We will describe the survival time distribution by treatment group using the Kaplan-Meier method. Also, we will compare the restricted mean survival times (RMST) between groups. The truncation time point for calculating the RMST will be 6 months, which will give us an estimate of 6-month lifetime expectancy for each group. We will estimate the difference in RMST and the corresponding 90% CI. The hazard ratio for death and its 90% CI will also be calculated if the proportional hazards assumption is reasonable. The determination of the violation of the proportional hazards assumption will be based on a significant p-value (<0.05) for the Grambsch and Therneau test.

- 4) *The Patient-Centered Experience of Anticoagulation QOL and Burdens*

- i) *Health Related Quality of Life (SF-12) at 3 and 6 months*

For SF-12, the primary analysis variable is the difference in the SF-12 mean change score from baseline. We will consider 2-point differences as clinically meaningful. We will use multiple imputations to handle missing observations. First, we will create 10 complete datasets, imputing missing values using chained equations, where we include measurements at baseline, 3 months, and 6 months. Second, we will estimate mean changes and the standard errors for each of the 10 complete sets. We will then use Rubin's method to derive an estimate for the difference in the mean change score

between two groups. Using the resulting estimate and the standard error, we will perform a Z-test to evaluate equality of SF-12 scores between groups.

*ii) Anti-Clot Treatment Scale (ACTS) score at 3 and 6 months*

For ACTS score, the primary analysis variables are the ACTS Burdens total score and the ACTS Benefits total score at month 6. We will consider 2-point differences as clinically meaningful. To minimize potential bias due to missing observations, we will allow and include surrogate estimates for all 3 patient-reported outcome assessments. Next, we will use multiple imputation to handle missing observations. First, we will create 10 complete datasets, imputing missing values using chained equations, where we include measurements at baseline, 3 months, and 6 months. Second, we will estimate mean changes and the standard errors for each of the 10 complete sets. Lastly, we will integrate the results using Rubin's method.

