### 13.3.5 Analyses for secondary endpoints

#### 1) *Cumulative rates of major bleeding reported by patients or clinicians at 6 months (NCI CTCAE Grade 3, 4, or 5)*

We will repeat the analogous analyses as performed for the primary endpoint (see 13.3.1). The primary analysis plan for major bleeding, fatal or non-fatal, is also based on the sequential evaluation of noninferiority and superiority. We will construct a two-sided 90% CI for the difference in the cumulative incidence rate for the composite outcomes of major bleeding and death. If the upper bound of the CI is less than 2.5%, we will conclude that DOAC is noninferior to LMWH/warfarin in terms of major bleeding. The same secondary analyses as planned for the primary endpoint will be performed. In contrast to clotting, fatal bleeding events are usually clinically manifest and recorded and therefore can be distinguished.

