## **2. Study overview**

### **2.1. Objectives**

The primary objective of the study is to compare the effectiveness of anticoagulation with a DOAC (intervention) with LMWH/warfarin (comparator) for preventing VTE recurrence in patients with cancer. The hypothesis is that the benefit of secondary prophylactic anticoagulation with a DOAC is not worse than the benefit from treatment with LMWH/warfarin based on cumulative VTE recurrence reported by patients or their clinicians at 6 months.

The secondary objectives are:

- 1) To compare the harms of DOAC vs. LMWH/warfarin therapy for cancer patients with VTE based on the cumulative rate of major bleeding at 6 months.
- Hypothesis: The harms from DOAC therapy are not worse than the harms from LMWH/warfarin therapy based on the cumulative rates of major bleeding reported by patients or clinicians at 6 months.
- 2) To compare the impact of DOAC vs. LMWH/warfarin therapy on the experience and burden of anticoagulation therapy for cancer patients with VTE.
  - Hypothesis A: DOAC and LMWH/warfarin therapy are associated with similar overall HRQOL (health-related quality of life) at 3 and 6 months.
  - Hypothesis B: DOAC therapy is superior to LMWH/warfarin based on the Anti-Clot Therapy Scale at 3 and 6 months.
- 3) To compare the impact of DOAC vs. LMWH/warfarin therapy on mortality in cancer patients with VTE
  - Hypothesis: The risks of all-cause and cause-specific mortality for cancer patients treated with DOAC therapy are not worse than the risks for those treated with LMWH/warfarin based on survival at 6 months.

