#### 3.5.2. Analysis for the primary endpoint

##### 3.5.2.1. Primary analysis

The primary aim of this study is to compare the intervention and comparator arms with respect to their ability to prevent recurrent VTE. Because the intervention (DOAC therapy) is more easily administered than the comparator (usual care with LMWH warfarin), DOAC is expected to have higher adherence and therefore decreased incidence of VTE. Accordingly, a noninferiority design with a superiority alternative is preferred, as described by Friedlen et al. The primary analysis will test the noninferiority of the DOAC therapy with the primary analytic cohort (modified ITT population of the randomized cohort). If noninferiority is demonstrated, superiority of the DOAC therapy will be tested.

Because VTE is often a proximate cause of death in cancer patients' unexplained sudden demise, but diagnostic procedures are rarely performed (post-mortem scans, autopsies, etc.), we considered VTEs that were clinically significant as the primary outcome on the basis of an antemortem diagnosis. Separately, we looked at all-cause deaths because deaths from cancer and deaths from VTE are difficult to distinguish. Cancer patients routinely die at home and it is not possible to determine whether the proximate cause of death was a VTE, progression of tumor or some other cause. Indeed, the cause of many deaths in cancer patients is multifactorial. We will estimate the cumulative incidence of recurrent VTE at 6 months using standard competing risk analysis methods, where death will be treated as a competing risk. We calculate the difference in the 6 months incidence rate between groups and the corresponding 0.90 confidence interval (CI).

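### The major-bleeding noninferiority rule is computed on major bleeding and death, with death unqualified, yet concludes on major bleeding alone

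*Combined protocol and SAP*

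**What the plan says.** The rule is in SAP 3.6.2, item 1: "We will construct a two-sided 90% CI for the difference in the cumulative incidence rate for the composite outcomes of major bleeding and death". Where the interval's upper limit falls below 2.5%, "we will conclude that DOAC is noninferior to LMWH/warfarin in terms of major bleeding". Protocol 13.3.5, item 1, has the same construction: "difference in the cumulative incidence rate for the composite outcomes of major bleeding and death".

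The rest of the plan names a narrower event.
- SAP 3.6.1 lists the endpoint as "Cumulative incidence of major bleeding reported by either patients or clinicians at 6 months".
- The harm hypothesis in SAP 2.1 is "based on the cumulative rates of major bleeding reported by patients or clinicians at 6 months".
- The heading of the item itself limits it to grades 3, 4 and 5.

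The same paragraph says to repeat the analyses of the primary endpoint. For recurrent VTE these use cumulative incidence, "where death will be treated as a competing risk" (SAP 3.5.2.1), and, as a secondary analysis, "we will handle deaths as censored observations and estimate the recurrent VTE event rates by the Kaplan-Meier method" (SAP 3.5.2.3, item 2).

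The paragraph ends by contrasting bleeding with clotting: "fatal bleeding events are usually clinically manifest and recorded and therefore can be distinguished".

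**The concern.** The interval is built on one event and the conclusion is drawn about another. Nothing says which deaths enter the composite. If all deaths do, the instruction to repeat the primary-endpoint methods cannot be followed, because a death cannot be both an event and a competing or censoring event.

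This is the only noninferiority rule for Objective 2. SAP 3.8.1 makes major bleeding the primary protocol safety endpoint, and SAP 3.8.2 sends its analysis back to 3.6.2. The lower-grade bleeding categories in item 2 copy the same analysis. Two analysts could follow the text in good faith, code different events and reach different verdicts on the main harm.

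**Working it through.** **Text.** The plan states no power, event rate or standard error for the bleeding test, so there is no figure to reproduce. The two readings compare as follows.

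| | Death = any death | Death = fatal bleeding |
|---|---|---|
| Event | Major bleeding or any death | Grade 3–5 bleeding |
| Agrees with endpoint and hypothesis | No | Yes |
| Death as competing risk or censored | Not possible | Possible for other deaths |
| Work done by adding death to the event | Changes it | None: grade 5 is already death (protocol 4.3, bleeding grades) |

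**Illustration of size.** Inputs from the documents: margin 0.025; two-sided 90% CI (z = 1.645); 671 randomized 1:1 (SAP 2.5), so n = 335 per arm. That n is an upper limit, since the modified ITT population is smaller and its size is not given. Assumed: major-bleeding risk b, death risk d, bleeding and death independent, no censoring.

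- Composite risk: p = b + d − bd
- SE = √[p₁(1−p₁)/n + p₀(1−p₀)/n]
- P(noninferior) = Φ((0.025 − (p₁ − p₀))/SE − 1.645)

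*No true difference.*

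| Event | p | SE | P(noninferior) |
|---|---|---|---|
| Bleeding, b = 3% | 0.030 | 0.0132 | 0.60 |
| Bleeding, b = 7% | 0.070 | 0.0197 | 0.35 |
| Composite, b = 3%, d = 10% | 0.127 | 0.0257 | 0.25 |
| Composite, b = 7%, d = 30% | 0.349 | 0.0368 | 0.17 |

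First row in full: SE = √(2 × 0.03 × 0.97/335) = 0.0132; 0.025/0.0132 − 1.645 = 0.25; Φ(0.25) = 0.60.

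With 275 per arm, to allow for a smaller modified ITT population, the ranges are 0.31–0.53 for bleeding and 0.15–0.22 for the composite. With deaths of only 2–5% at n = 335, the composite gives 0.26–0.44.

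Non-bleeding deaths make up d(1−b)/p of composite events: 57–91% with deaths of 10–30%, and 21–62% with deaths of 2–5%.

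*Disagreement between readings.* 200,000 simulated trials per scenario, no true difference, n = 335:

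| b, d | Verdicts differ | Bleeding passes, composite fails | Composite passes, bleeding fails |
|---|---|---|---|
| 7%, 10% | 0.27 | 0.20 | 0.06 |
| 7%, 30% | 0.33 | 0.26 | 0.07 |
| 4%, 22% | 0.43 | 0.38 | 0.05 |
| 3%, 10% | 0.44 | 0.39 | 0.05 |
| 3%, 30% | 0.52 | 0.47 | 0.04 |

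With deaths of 2–5% the verdicts differ in about 15–36% of trials.

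*True bleeding excess.* P(noninferior) is now the chance of a false conclusion about bleeding.

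| Deaths, DOAC vs control | Bleeding 6.5% vs 4% (at margin) | Bleeding 8% vs 4% |
|---|---|---|
| Bleeding-only rule | 0.050 | 0.007 |
| Composite, 22% vs 22% | 0.069 | 0.034 |
| Composite, 20% vs 22% | 0.18 | 0.10 |
| Composite, 18% vs 22% | 0.36 | 0.23 |
| Composite, 14% vs 22% | – | 0.67 |

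With equal deaths of 10–30%, the figure at the margin is 0.060–0.075. The small inflation follows from independence: the composite difference shrinks to (b₁ − b₀)(1 − d), for example 0.025 × 0.78 = 0.0195 at d = 22%. If non-bleeding deaths are instead fixed and equal as a separate category, the composite difference stays at 0.025 and the rate stays at 0.05.

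**The case against.** The best defence is that the paragraph points to fatal bleeding. It describes the endpoint as covering bleeding whether or not it kills, and its last sentence explains why bleeding deaths, unlike clotting deaths, can be identified. That remark has no purpose if every death counts. All-cause death has its own item with no confirmatory test, and carrying the literal reading into item 2 would give nuisance bleeding or any death, which makes little sense. On this view the import of the primary-endpoint methods, the heading and the endpoint list already imply the right analysis.

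Much of this stands. Fatal bleeding is a plausible intention, and if it was meant, none of the numerical effects arises and the change is one of wording. It is also fair that all the figures rest on assumed rates, that with equal mortality the literal rule mostly errs towards failing to show noninferiority (roughly 76–92% of the discordant simulated trials), and that serious masking needs lower mortality on DOAC together with more bleeding. The primary VTE test is untouched, and the separate mortality analysis and the safety monitoring give a reader other evidence.

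It does not rescue the rule. No sentence limits the deaths to bleeding deaths, and none states how other deaths are handled in the bleeding interval. A prespecified decision rule should not depend on the analyst inferring the event from its surroundings.

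**Conclusion.** The concern holds. As written, the rule tests major bleeding or death and concludes on major bleeding, against the plan's own endpoint, hypothesis and competing-risk method. This rests on the text and not on the calculations.

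The calculations show that the choice matters if the words are followed literally. Under the assumed rates with deaths of 10–30%, the chance of showing noninferiority falls from 0.35–0.60 to 0.17–0.25. At a true excess equal to the margin, false noninferiority stays near nominal with equal mortality and rises to 0.18 or 0.36 if DOAC mortality is 2 or 4 points lower (against 22%). The corrected test would still not be well powered at a 2.5% margin. The point must be settled before analysis because it governs the only noninferiority conclusion on the trial's main harm.

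**What to change.** In SAP 3.6.2, item 1, and protocol 13.3.5, item 1, replace the composite with: major bleeding (CTCAE grade 3–5, fatal or non-fatal), with death not due to bleeding as a competing risk. Apply the 2.5% margin to that difference in 6-month cumulative incidence.

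Carry the same principle into item 2 of both sections: bleeding of the stated grade is the event, and death not due to bleeding is a competing risk. If bleeding-or-death is of interest, keep it as a labelled sensitivity analysis that supports no conclusion about bleeding.

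The alternative, making the composite the endpoint and rewording the conclusion, would be coherent but would change Objective 2 and leave it without a test of bleeding.

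The cost is wording in two documents. No new data are needed: deaths are reported with attribution and grade 3–5 bleeds are reported under protocol 12.3, and major bleeds are adjudicated blind to treatment under protocol 13.10.
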